## 2.4 Treatments (study treatment, rescue medication, concomitant therapies, compliance)

### 2.4.1 Study treatment / compliance

The study treatment is single injection of MIJ821 (10mg, 4mg or 1mg) or placebo on Day 1, the number of patients completed treatment will be reported by treatment arm based on SAF. Patients with protocol deviations related to treatment will be summarized in the PD summary table.

In case of unblinding during the study, any efficacy-related PRO data (including MADRS, [REDACTED]) collected after unblinding will be removed from the corresponding analysis. All safety data (including AE and safety-related PRO data) will be included in the corresponding analysis.

### 2.4.2 Prior, concomitant medications and non-drug therapies

For the standardization of data display, all the prior and concomitant medications reported on eCRF page will be coded using the World Health Organization (WHO) drug dictionary, which employs the Anatomical Therapeutic Chemical classification (ATC) system. The version of the dictionary used will be reported in the TFL outputs.

Non-drug therapies or procedures will be coded by Medical Dictionary for Regulatory Activities (MedDRA).

All analysis for prior and concomitant medications will be performed based on the safety set SAF.

The prior medications/non-drug therapies are defined as drugs/non-drug therapies taken and stopped before the start of the study treatment on Day 1. Concomitant medications/non-drug therapies are defined as drugs taken at least once after the study treatment on Day 1.

For missing start or stop dates of the reported medications, the dates will be imputed using Novartis standards (Section 5.1.3).

Prior and Concomitant medications will be summarized separately based on ATC code (level 1 and level 3), preferred term and treatment arm.

Prior MDD-related medications will be summarized based on ATC code (level 1, 3 and 4), preferred term and treatment arm.

Prior and Concomitant non-drug therapies will be summarized separately by primary system Organ Class and preferred term.

#### **2.4.2.1 Current Standard of care (SoC) and psychotherapy use**

Current standard of care (SoC) is identified as (1) medications flagged as “MDD related medications” on the ‘prior or concomitant medication’ e-CRF page, (2) ongoing during treatment (i.e. started before first dose of study drug and ongoing thereafter) and (3) the medication is either an antidepressant (ATC3=“ANTIDEPRESSANTS”) or an augmentation drug as confirmed by clinical review.

[figure not shown]
Psychotherapy is allowed to be used and needs to be stable during the study. Current allowed MDD related procedure (Psychotherapy) is identified as (1) flagged as “MDD related procedures” on the ‘prior or concomitant non-drug therapies/procedures’ e-CRF page, (2) is NOT listed in the prohibited medication table ([Table 6-2] in the protocol) and (3) ongoing during treatment (i.e. started before first dose of study drug and ongoing thereafter).

Current standard of care (SoC) medications will be summarized by ATC code level 1, 3 and 4 and preferred term and by treatment arms. Current allowed MDD related procedure will be listed by treatment arms.

#### **2.4.2.2 Intercurrent events**

Medical review will be conducted to identify intercurrent events (IE) with onset happen post-dose, especially before the 24 hours post-dose assessment of the primary outcome (MADRS score). A listing of any new/change in medication/therapies post the treatment will be generated for this purpose and the records happened within 24 hours post-dose will be marked. Intercurrent events may include:

- New intake or change in baseline SoC medications/therapies which have a potential confounding effect.
- Intake of prohibited medication/ therapy [REDACTED]
- Intake of rescue medications.

The rescue medications are identified by clinical judgement based on documented usage and indication of the drug. List of rescue medications (if any) identified by clinical team during medical review before DBL will be used in the CSR outputs.

The listing of concomitant medications and therapies which qualify as intercurrent events with onset after injection on Day 1 will be provided and the records within 24 hours post-dose will be marked. The '24 hours post-dose' will be based on the actual assessment date/time of the efficacy outcome on Day 2. Different flags will be used to mark different IEs. For SoC changed before 24 hours post-dose assessment, all records of the same drug will be listed and the first record of change will be flagged. For prohibited/rescue medications, any use during 24 hours post-dose will be flagged.

## 2.5 Analysis supporting primary objective(s)

The primary efficacy analysis will be conducted after all required data are collected and cleaned.

The primary clinical question of interest is: What is the effect of s.c. MIJ821 versus placebo in addition to SoC at 24 hours after the injection of the study drugs on change in depressive symptoms measured by MADRS total score in participants with treatment resistant depression (TRD), who have already failed to adequately respond to at least two conventional antidepressants, while accounting for intercurrent events (IEs) with potential confounding effects and IEs leading to study discontinuation prior to 24 hours?

### 2.5.1 Primary estimand and endpoint(s)

The **primary estimand** is described by the following attributes:

1. Population: participants with treatment resistant depression, who have failed to show adequate treatment response to at least 2 antidepressants previously.
2. Primary variable: change from baseline in MADRS total score at 24 hours post-dose
3. Treatment of interest: the randomized treatment (the investigational treatment MIJ821 or the placebo treatment) administered as a single s.c. injection on Day 1. The dose of the allowed concomitant medication (SoC) for depression must remain stable after baseline and during the trial.
4. Intercurrent Events (IEs) prior to MADRS assessment at 24 hours.  
IEs with potential confounding effect prior to the 24-hour assessment:
  - New intake or change in concomitant medications/therapies which have a potential confounding effect.
  - Intake of prohibited medications/therapies.
  - Intake of rescue medication.
  - Pandemic related IEs.
  - IEs leading to study discontinuation prior to the 24-hour assessment:
    - Adverse events (AE).
    - Lack of efficacy (LoE).
    - Other reasons for study discontinuation.
5. The summary measure: treatment difference in variable means between study drug and placebo.

The **primary endpoint** is the change from baseline in MADRS total score at 24 hours post study treatment.

#### 2.5.1.1 Derivation of MADRS total score

The MADRS consists of 10 items that cover all the core depressive symptoms (apparent sadness, reported sadness, inner tension, sleep, appetite, concentration, lassitude, interest level, pessimistic thoughts, and suicidal thoughts). Each item is scored from 0 (item is not present or is normal) to 6 (severe or continuous presence of the symptom). For each item, a higher score represents a more severe condition.

The MADRS score will be measured at Screening, Baseline (Day 1, -1 hour), 4-hour post-dose on Day 1, 24 hours post-dose and follow-up visits on Day 8, Day 15, Day 22 and Day 29 (EOS).

The 4-hour post-dose assessment will use the '4-hour' questionnaire which is based on participant's condition as observed over the past 4 hours. Two items (reduced sleep and reduced appetite) are not applicable for 4-hour post-dose assessment and will be imputed based on the value of respective 1-hour pre-dose assessment.

[figure not shown]
The 24 hours post-dose assessment is based on the participant's condition as observed since the last evaluation. For all other assessments, a 7-day recall period is used.

A total score (ranges from 0 to 60) is calculated by adding the scores of all 10 items. The following proration formula will be applied to calculate the total score in the case when one of the item scores is missing:

[figure not shown]
$$\text{Total score} = \text{Sum of scores from items present} * (10 / \text{number of items present}).$$

Otherwise if 2 or more items are missing, the total score will be set to missing.

[REDACTED]

[REDACTED]

[REDACTED]

[REDACTED]

[REDACTED]

#### **2.5.4 Handling of missing values not related to intercurrent events**

For other missing outcomes caused by reasons other than IEs, multiple imputation approach will be applied assuming MAR for all treatment arms.

[REDACTED]

[REDACTED]

[REDACTED]

[REDACTED]

[REDACTED]

[REDACTED]

[REDACTED]

## 2.6 Analysis supporting secondary objective(s)

### 2.6.1 Efficacy endpoint(s)

#### 2.6.1.1 Duration of antidepressant effect of MIJ821

##### Change from baseline in the MADRS total score over time

Derivation of the MADRS total score is covered in [Section 2.5.1.1](#). The change from baseline in MADRS total score will be summarized for all collected data (including 4-hour post-dose) by visit/timepoint and by treatment arms. In case of unblinding, the MADRS scores collected after patient's unblinding will be excluded in all the analysis. A listing of MADRS total score for each participant at each visit will be provided by treatment arm.

The change from baseline in MADRS total score at follow-up visits on Day 1 4 h post-dose, Day 2, 8, 15, 22 and 29 will be analyzed using the mixed-effects model for repeated measures (MMRM). This model will include the fixed, categorical effects of treatment, time (i.e. analysis visits), baseline MADRS score, class of anti-depressant standard of care, treatment-by-time and baseline MADRS score-by-time interactions. [REDACTED]

A summary table with model estimated means and their differences of each MIJ821 doses vs. placebo, will be obtained at each visit/timepoint, along with the 90% CI for the difference. Model estimated treatment means in change from baseline in MADRS score ( $\pm$ SE) will be plotted over time/visit for each arm.

[REDACTED TABLE]

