Data analysis	To assess the efficacy, change from baseline in the MADRS score at 24 hours after single s.c. injection will be analyzed using an analysis of covariance (ANCOVA) model with treatment as a group factor, class of antidepressant and baseline MADRS as a covariates, the Multiple Comparison Procedure - Modeling (MCP-Mod) methodology will be used to test the null hypothesis of a flat dose-response for the primary efficacy endpoint at a one sided significance level of 5% against the alternative hypothesis of a non-constant dose-response curve. If dose-response signal is detected, the MCP-Mod methodology, will also be employed to investigate the dose-response relationship.
Key words	Treatment-Resistant Depression; Major Depressive Episode; Major Depressive Disorder

1 Introduction

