12.5 Analysis supporting secondary objectives

12.5.1 Efficacy and/or Pharmacodynamic endpoint(s)

Duration of antidepressant effect of MIJ821

To assess the efficacy of antidepressant effect of MIJ821 over time, the following secondary endpoints will be evaluated:

- The change from baseline in the total MADRS score at Day 2, 8, 15, 22 and Day 29 visits after s.c. administration will be analyzed using the mixed-effect model for repeated measures (MMRM). This model will include the fixed, categorical effects of treatment, time (i.e. analysis visits), baseline MADRS score, class of anti-depressant standard of care, treatment-by-time and baseline MADRS score-by-time interactions. An unstructured (UN) covariance structure will be used to model the within-subject variability. More details of this analysis will be specified in SAP.
- Number (percentage) of participants who discontinued study due to lack of efficacy or need for new antidepressant treatment (pharmacological or psychotherapy) will be summarized by treatment arms.

Dose-response relationship of MIJ821

The assessment for the dose-response relationship of MIJ821 and estimation of the target dose will be based on the estimated dose-response curve derived from the MCP-Mod methodology in primary analysis (see Section 12.4.2).

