### **2.3.2 Demographics and other baseline characteristics**

Demographic variables and other baseline characteristics will be summarized for each randomized treatment arm and for all participants (total) based on Randomized set.

Participant demographic and baseline characteristics will include:

- Age
- Sex
- Ethnicity
- Race
- Height
- Weight
- BMI and BMI group (<25; >=25 and <30; >=30)
- Employment status
- Social status
- Region (USA, Europe, Japan)

Disease characteristics at baseline will include:

- Drug class of baseline antidepressants: Selective Serotonin-Reuptake Inhibitors (SSRIs); Serotonin-Norepinephrine Reuptake Inhibitors (SNRIs); Other antidepressants or any combinations

- Baseline SoC category: Antidepressant in monotherapy; Antidepressants in combinations; Antidepressants + Augmentation
- CYP2D6 metabolizer phenotypes classifications (Ultrarapid metabolizers, Normal metabolizers, Intermediate metabolizers, Poor metabolizers)
- Baseline MADRS score and category (<30, 30-34, 35-40, >40)
- Disease duration (years) derived as (randomized date – Date MDD first ever diagnosed) / 365.25
- Duration of current depressive episode (weeks) derived as (randomized date – onset date of current depressive episode) / 7
- Total number of major depressive episodes in lifetime (excluding the current episode): 1, 2, 3-5, >5
- Overall severity of current episode (mild, moderate, severe, not reported)
- Overall severity of the first episode (mild, moderate, severe, not reported)
- Hospitalization events for current episode (Yes/No)
- Does the participant have any biological relatives who have or had diagnosis of Psychiatric disorder (yes, no)
- Current major depressive episode features
  - Anxious distress (yes/no)
  - Mixed features (yes/no)
  - Melancholic features (yes/no)
  - Atypical features (yes/no)
  - Catatonia (yes/no)
  - Seasonal pattern (yes/no)
- Number of failed antidepressant treatments prior to screening in current MDE (<3, >= 3).
- Reason for discontinuation of prior MDD related medication/therapies (due to lack of efficacy, adverse event, non-compliance, no longer required, others).

The antidepressant category of patients at baseline is summarized based on the actual baseline ADs collected in eCRF CM page, in the case that patient has no baseline antidepressant reported, the randomization strata from the IRT system will be used.

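### The secondary MMRM sentence in SAP 2.6.1.1 and Protocol 12.5.1 lists baseline MADRS score and baseline-by-time as categorical effects; both should be called continuous covariate terms

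*SAP*

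**What the plan says.** The model for change in MADRS over time is described in SAP 2.6.1.1: "This model will include the fixed, categorical effects of treatment, time (i.e. analysis visits), baseline MADRS score, class of anti-depressant standard of care". The same list ends with "treatment-by-time and baseline MADRS score-by-time interactions". Protocol 12.5.1 carries the same sentence.

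In the protocol, the text that follows is visible. It says "An unstructured (UN) covariance structure will be used to model the within-subject variability" and then "More details of this analysis will be specified in SAP". In the SAP, the text directly after the sentence is redacted.

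The model's output, per SAP 2.6.1.1, is a set of model means and differences of each dose from placebo, which "will be obtained at each visit/timepoint, along with the 90% CI for the difference".

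Three other places bear on the intended coding:

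- SAP 2.5.1.1 defines the MADRS total as the sum of ten items, ranging from 0 to 60. It is prorated by 10/9 when one item is missing.
- The Data analysis row of the Protocol summary describes the primary ANCOVA with "treatment as a group factor, class of antidepressant and baseline MADRS as a covariates".
- SAP 2.3.2 lists, for the descriptive baseline summary, "Baseline MADRS score and category (<30, 30-34, 35-40, >40".

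**The concern.** One adjective, categorical, governs the whole list, and baseline MADRS is not a categorical variable. Read literally, every distinct baseline score becomes a class level and the interaction repeats those levels at each visit. A prorated total need not be an integer, so it could form a level of its own.

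The visible words leave three codings open: one slope per visit, the four groups used in the baseline summary, or one level per score. A model sentence that programmers and validators implement should allow only one.

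What is at stake is the precision of the secondary duration-of-effect estimates in a trial with about 14 participants per arm. The reach is limited. Protocol 12.5.1 states that "estimation of the target dose will be based on the estimated dose-response curve derived from the MCP-Mod methodology in primary analysis", so the target dose does not rest on this model. No test or decision rule is visible for the MMRM.

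**Working it through.** **No stated figure to reproduce.** No number in the plan depends on this wording. The stated power of about 90% concerns the primary MCP-Mod test, and its candidate curves, effect size and SD are not in the visible text.

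**Which coding do the passages support?** SAP 2.3.2 names the score and the category as two different things, and the MMRM sentence uses the score, with no cut-points. The Protocol summary sets baseline MADRS apart from the treatment factor by calling it a covariate. That is weaker evidence, because antidepressant class, which is categorical, is called a covariate in the same phrase. Together they favour a continuous intent without stating it.

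**Inputs from the documents.** 56 participants, 14 per arm (SAP 3); four arms; three antidepressant classes (SAP 1.1); baseline MADRS at least 24 (Protocol 5.1); six post-dose timepoints (SAP 2.6.1.1: 4 hours, Days 2, 8, 15, 22 and 29); 90% intervals.

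**Assumptions, not in the documents.** Complete data; integer baselines from a normal distribution truncated at 24; a random mix of the three classes; equal residual variance under each coding.

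**Degrees of freedom at one visit.** The model has an intercept (1), treatment (3), class (2) and b baseline terms:

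residual df = 56 − (1 + 3 + 2 + b) = 50 − b

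- One slope: b = 1, so df = 49. Over six visits there are 6 baseline parameters.
- One level per score with L distinct scores: b = L − 1, so df = 51 − L. Over six visits there are 6(L − 1) baseline parameters.
- Four summary groups: b = 3, so df = 47. Over six visits there are 18 baseline parameters.

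**Interval width.** The half-width is t(0.95, df) × s × √c, where c is the diagonal element of (X′X)⁻¹ for the dose effect. At equal s:

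width ratio = [t(0.95, 51 − L) / t(0.95, 49)] × √(c_levels / c_slope)

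Averages over 3,000 simulated designs per row, one level per score against one slope:

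| Baseline mean / SD | Distinct scores L | Residual df (from 49) | SE ratio | 90% CI width ratio | Baseline parameters, six visits (from 6) |
|---|---|---|---|---|---|
| 30 / 4 | 14.6 | 36.4 | 1.161 | 1.169 | 82 |
| 33 / 5 | 18.2 | 32.8 | 1.226 | 1.238 | 103 |
| 35 / 6 | 20.8 | 30.2 | 1.274 | 1.290 | 119 |

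Check on the middle row: 51 − 18.2 = 32.8; 6 × (18.2 − 1) = 103; 1.238 / 1.226 = 1.01. Nearly all the widening therefore comes from the standard error, and about 1% from the t quantile.

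**Wider range.** Fifteen settings (mean 30, 32 or 35; SD 3 to 7) give about 13-22 levels, residual df of about 38 down to 29, and 70-128 baseline parameters over six visits. On average 2-7 of the 56 participants are alone at their score, so their own level absorbs their data at each visit. The median width ratio is 1.13 at 30/3, 1.22 at 32/5 and 1.32 at 35/7 (1.14 to 1.33 by the mean).

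**Six-visit check.** Generalised least squares with the SAP terms and five known covariance patterns gives a contrast SE 11-32% larger with complete data. At Day 29 it is 12-34% larger with 10% assumed dropout and 14-38% larger with 20%. No MMRM with an estimated unstructured covariance was fitted, so nothing is claimed about convergence.

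**The case against.** The strongest reply is that nobody would fit the literal model. It needs some 70-128 baseline parameters for 56 participants, it names a score and gives no levels, and the adjective most likely just runs past the terms it fits. The SAP text where the coding would be stated is redacted, and the protocol defers detail to the SAP, so the sponsor may already have it right. If categorical were meant, the four groups in SAP 2.3.2 are an obvious candidate. They would widen the 90% CI by only about 1-2% from the design alone, plus 1-4% from coarser adjustment if baseline and outcome correlate at 0.3-0.5 (assumed).

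Most of this stands, and it is why the point is minor. The 13-32% range belongs to one reading, which is not the likely intent, and its baseline distribution is assumed. What does not follow is that the text can stay. Redacted text cannot be counted against the plan, but the visible SAP sentence is wrong as written whatever comes next. In the protocol, the sentences that follow are visible and do not correct it.

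**Conclusion.** The sentence is wrong as written in both documents and is probably a drafting slip. The size depends on the coding used:

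- **Continuous, the likely intent:** no cost.
- **The four summary groups:** about 1-2% wider 90% CIs from the design, with a few percent more from coarser adjustment.
- **One level per score, the literal reading:** about 13-32% wider at a single visit with complete data.

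The last two figures rest on an assumed baseline mean, SD and class mix, and the design-only widening also on equal residual variance. The effect is confined to the secondary estimates of each dose's difference from placebo over time. The primary analysis, sample size, alpha and target-dose estimate are not shown to be affected. Severity is minor. Confidence is medium, because the redacted SAP text may already settle the coding.

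**What to change.** Reword the model sentence in SAP 2.6.1.1, for example: *fixed categorical effects of treatment, visit, antidepressant class and treatment-by-visit; baseline MADRS total score and baseline-by-visit as continuous covariate terms*. Visit itself stays categorical, so the interaction gives one baseline slope per visit. If the redacted text already says this, only the visible sentence needs correcting.

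Make the same change in Protocol 12.5.1. Protocol 14.1 requires a written amendment for any protocol change, so this can wait for the next one. An entry in SAP section 4 is optional, because this is a clarification.

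The cost is one SAP sentence. A continuous term assumes a linear relation with baseline at each visit. If that is wrong, randomisation still protects the treatment contrast and the loss is some precision.

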## 2.7 Safety analyses

The safety and tolerability of MIJ821 will be evaluated by adverse events, clinically significant findings from laboratory test, physical examination, vital signs, 12-lead ECG. Abnormal findings from safety scales will be reported as adverse events and analyzed accordingly. For all safety analysis, the safety set (SAF) will be used. All listings and tables will be presented by treatment arm.

The treatment-emergent period will be defined as starting from the date of administration of study treatment to EOS visit. Safety summaries (tables, figures) include only data from the on-treatment period with the exception of baseline data which will also be summarized where appropriate (e.g. change from baseline summaries). In particular, summary tables for adverse events (AEs) will summarize only on-treatment events, with a start date during the on-treatment period (treatment-emergent AEs). Treatment-Emergent Adverse Events (TEAEs) in this study are defined as adverse events starting or worsening after the administration of study medication and up to the EOS visit. That is, all the reported AEs collected post treatment will be considered as TEAEs, so we will simply use AEs all through this section to avoid any confusion.

